1.0 BACKGROUND AND RATIONALE

1.1 Proton Beam Therapy

Proton beam therapy (PT) is a rapidly evolving modality with high potential for improving radiation therapy clinical outcomes because of its ability to deliver high doses to the target tissue while sparing surrounding normal tissues. Because of the finite range of protons in tissue, proton dose rapidly peaks at a maximum value (call the “Bragg Peak”) near the end of the charged particle range and then abruptly falls to negligible levels. By properly modulating the proton energy, and superposing many Bragg Peaks (the “spread-out Bragg peak” or SOBP), a single-field dose distribution is created which uniformly treats the tumor and falls to negligible levels within a few mm beyond the distal tumor margin, thereby sparing almost completely normal tissues located distal to the tumor. However, PT dose delivery is very sensitive to the physical characteristics of the tissues in the beam’s path. Both the magnitude and position of the Bragg peak depends on the composition and density tissue of tissues traversed by the protons. Recommended {ICRU, 1989 #1028; ICRP, 2003 #904} organ/tissue compositions and densities, available for radiotherapy planning, are based upon historic (mostly from 1930-1960) tissue sample measurements {White, 1988 #1030; Woodard, 1986 #1031; Hammerstein, 1979 #1032} with large variations within the suggested values {Brooksby, 2006 #1052; Dance, 1999 #1033; Geise, 1996 #993}. These are potentially imprecise values that may vary significantly from patient-to -patient and within a single patient. Due to the aforementioned uncertainties in tissue composition and density, it is customary to add a 3.5% (about 4 mm for 12 cm range protons) to ensure adequate tumor coverage in the face of these so-called proton range uncertainties. Unfortunately, these safety margins significantly reduce the potential for sparing normal tissue.

Mitigating PT range uncertainties through more accurate characterization of tissue density and composition variability would support of more accurate prediction of dose delivered to the tumor target and adjacent normal tissues. Current PT planning practices rely on standard single-energy CT imaging (SECT) which necessitates 3-6 mm range uncertainty margins {Moyers, 2001 #1843; Zhang, 2007 #1844} that significantly increases exposure of adjacent organs to high doses. In theory, dual-energy CT imaging (DECT) can reduce the range uncertainty problem encountered within PT by non-invasively and more accurately measuring the radiological tissue properties needed to perform accurate PT dose calculations {Yang, 2010 #1853; Williamson, 2006 #923}. However, as currently configured, commercial CT scanners cannot support the level of measurement accuracy required by DECT analysis {Williamson, 2006 #923} to significantly reduce range uncertainty margins .

1.2 Study Rationale

The aim of this protocol is to refine the accuracy of PT by the use of DECT, in conjunction with novel iterative image reconstruction algorithms, to more precisely determine the tissue properties through which the proton beam path travels.

Plan quality in proton therapy is compromised by lack of accurate knowledge of proton stopping power, giving rise to dose prediction errors (DPEs) and optimization-convergence errors (OCEs). The DPEs are defined as the difference between the dose calculated by the treatment planning system and the actual dose delivered to the patient, mainly affected by the inaccurate prediction in the distal edge of a proton beam. OCE is defined as the difference between a clinically executed plan produced by an optimizer based on dosimetric approximations (e.g., SECT) and a better plan (e.g., based on DECT). Accounting for inaccuracies or uncertainty in proton stopping power, the planning optimizer must include a safety margin for the resulting range uncertainty and perform robust optimization using the distribution of errors. We hypothesize that both DPEs and OCEs arising from SECT SP mapping errors will give rise to measurable changes in clinical outcomes and that this loss of clinical efficacy can be reduced with more accurate estimation of proton stopping power using DECT.

Knowledge gained from the DECT will be used to generate a mock PT plan for comparison purposes. Successful completion of this project is intended to measure potential increases in the accuracy with which cancers can be treated with proton therapy and to reduce the potential incidence of normal tissue toxicity. We will then evaluate whether the additional normal tissue dose sparing achieved in these mock plans could improve outcomes for patients undergoing proton therapy by reducing normal tissue complications or enabling tumor dose escalation in comparison to the more traditional 3-6 mm estimates of range uncertainty from Moyer et al.

Uncertainty in proton range is incorporated into proton plan optimization in two ways: safety margin and robust optimization. Safety margin involves expanding CTV and OAR contours (generally by 3.5% of proton range) as recommended by ICRU 50 and 62. Recent studies have demonstrated that robust optimization in proton therapy produces more consistent and predictable dose distribution through the whole treatment course. Given the PDFs describing various uncertainties (setup, organ motion, and true vs. apparent SPR values), robust optimization selects multiple worst case scenarios (instances of patient anatomy and SPR assignments) from the ensemble of all possible instances described by the PDFs. The optimizer then optimizes the plan to satisfy the planning constraints and goals simultaneously on the multiple worst-case scenarios. The resultant plan is robust in the sense that acceptable outcomes will be realized even in the face of the most unfavorable random outcomes (positioning and SPR errors) that are likely to occur. In clinical practice, volumetric imaging greatly reduces the uncertainty associated with setup and sheds light on pre-treatment reoptimization of the treatment plan. As the range uncertainty becomes the largest uncertainty in plan optimization, accurate information on proton stopping power helps the optimizer achieve a more optimal plan.

Patient participation will be limited to having a DECT instead of the standard SECT. That single DECT session will be used to generate two treatment plans; one using standard range uncertainty margins and the second using exact measures of tissue density from the DECT to generate a mock treatment plan for comparison. We expect that the mock treatment plan will have tighter margins around the tumor and spare more normal tissue. Eligible patients

will either have lung cancer or cancer of the brain or base of skull. We have chosen these two patient populations because the tumor is adjacent to air densities where range uncertainty is greater, the problem poses the greatest technical challenge, and reducing the projected toxicity to critical structures would be clinically most meaningful (i.e. reducing dose to the esophagus or optic nerve).

Application of novel CT imaging systems to human patients will allow their performance to be evaluated in a clinical context in ways that cannot be duplicated in phantoms or non-human models. By using human subjects, this research proposal is able to investigate the accuracy of dual-energy CT in the calculation of SPRs that significantly affect the outcome of patients treated with proton therapy.

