1.3 CT scanning equipment

State-of-the art commercially marketed CT simulators in the Department of Radiation Oncology will be used to acquire the research data needed for these projects. Currently, the systems available to this project include the Philips Brilliance Big Bore CT/simulator (16 detector rows and 85 cm bore) and the Siemens Confidence CT/simulator (20 detector rows and 80 cm bore).

In addition to acquiring medically-routine CT datasets, each patient subject will be scanned sequentially at two or three different beam energies (80 or 90 kVp, 100 kVp, 120 kVp, and/or 140 kVp) as part of this research study. These additional scans will be acquired utilizing the FDA-approved workflow and scanner operating modes. Sinogram data will be exported in raw, minimally processed form utilizing proprietary data export and processing tools provided to the investigators by the scanner vendors. In no case, will the additional local imaging dose (in terms of CTDI_{vol}) given to the patients by the two or three additional scans exceed 6 cGy per session.

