5.0 STUDY PLAN

5.1 Experimental procedures and data to be acquired

Patient therapy will not be affected by enrollment in this study. Patients enrolling in this study will undergo additional sequential DECT scans in addition to their routine SECT or DECT scans by enrolling in this study, which will increase imaging dose to the patients. An additional two sequential scans of the thorax or H&N/brain will be acquired at scan settings ranging from 70kVp to 140 kVp (with or without additional filter) prior to initiating RT. Typically, the experimental DECT imaging data will be acquired prior to the clinically-necessary CT simulation study in the same session. Up to two additional experimental DECT imaging sessions should be scheduled when logistically feasible. For example, if a patient subject requires re-simulation, DECT scan data should be acquired prior to the clinical simulation study in the same session. Raw sinograms without beam-hardening or scatter corrections will be exported from the scanner and archived with the vendor's support. In addition, clinical SECT and DECT images acquired as part of routine RT planning will be collected for this study. For H&N and brain patients, the DECT scan volume should extend from the superior-most aspect of the cranium down to the suprasternal notch. For the thoracic patients, the scan volume should encompass the entire lung parenchyma (apices to base).

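### Does Section 1.2's account of one DECT session in place of the standard CT, set against Section 5.1's added scans and repeat sessions, call for a change to the plan?

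*Combined protocol and SAP*

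**What the plan says.** Section 1.2 (Study Rationale) states: "Patient participation will be limited to having a DECT instead of the standard SECT. That single DECT session will be used" to produce a plan with standard margins and a mock plan for comparison.

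Section 1.3 (CT scanning equipment) treats the research imaging as extra: "In addition to acquiring medically-routine CT datasets, each patient subject will be scanned sequentially at two or three different beam energies". The settings it lists are "two or three different beam energies (80 or 90 kVp, 100 kVp, 120 kVp, and/or 140 kVp". It caps the local dose from the two or three extra scans at 6 cGy per session.

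Section 5.1 (Experimental procedures and data to be acquired) says that enrolled patients "will undergo additional sequential DECT scans in addition to their routine SECT or DECT scans", and that this raises their imaging dose. On content and timing it says:

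- On the research scans: "An additional two sequential scans of the thorax or H&N/brain will be acquired at scan settings ranging from 70kVp to 140 kVp" before radiotherapy starts.
- On their place beside the clinical scan: "Typically, the experimental DECT imaging data will be acquired prior to the clinically-necessary CT simulation study in the same session".
- On the clinical images themselves: "clinical SECT and DECT images acquired as part of routine RT planning will be collected for this study".
- On repeat acquisitions: "Up to two additional experimental DECT imaging sessions should be scheduled when logistically feasible".

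Section 6.1 (Potential Risk) describes the research dose as additional, below 6 cGy per session and no more than 24 cGy over the treatment course. It puts the risk at 0.0002 excess cancers per cGy over 30 years. Section 6.2 (Protection against Risk) also speaks of increased imaging and sets it beside therapeutic doses of 30-90 Gy.

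**The concern.** Taken literally, Section 1.2 swaps one kind of CT for another, once. Section 5.1 keeps the clinical CT, adds research scans to it and allows the research session to be repeated. A scan cannot both replace the routine CT and be added to it, and one session is not up to three. Two smaller differences appear beside this. The lowest tube voltage is 80 kVp in Section 1.3 and 70 kVp in Section 5.1, and Section 1.3 allows a third scan that Section 5.1 does not mention.

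What would be at stake is the description of burden and radiation exposure. If Section 1.2 were the account that people worked from, the added exposure would be understated. If the dose limits or the risk statement had been built on a single replacement scan, they would not cover what Section 5.1 permits. A statistician would also ask whether the number of acquisitions enters the analysis or the sample size.

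**Working it through.** **1. Replacement or addition.** Five sections bear on this:

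| Section | Research DECT relative to routine CT |
|---|---|
| 1.2 | replaces the standard SECT |
| 1.3 | added |
| 5.1 | added; clinical simulation still performed |
| 6.1 | dose described as additional |
| 6.2 | imaging described as increased |

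Four sections agree and one rationale paragraph differs. The section that staff follow to acquire the scans is among the four.

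**2. Number of sessions.** Section 1.2 gives 1. Section 5.1 gives 1 initial + up to 2 further = up to 3. The count of three comes from Section 5.1 alone, because Section 1.3 gives only a per-session dose cap. These need not be extra visits, since Section 5.1 typically places the research scans in the clinical simulation session and offers re-simulation as its example of a repeat.

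**3. Dose limits.** Inputs are 6 cGy per session (Sections 1.3 and 6.1), 24 cGy in total and 0.0002 per cGy (Section 6.1). Upper bound on added dose = sessions × 6 cGy; upper bound on risk = dose × 0.0002.

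| Case | Added dose, at most | Risk at 0.0002 per cGy |
|---|---|---|
| 1 session | 1 × 6 = 6 cGy | 6 × 0.0002 = 0.0012 |
| 3 sessions | 3 × 6 = 18 cGy | 18 × 0.0002 = 0.0036 |
| Stated total | 24 cGy | 24 × 0.0002 = 0.0048 |

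The largest exposure under Section 5.1 is 18 cGy, which is below 24 cGy. The stated total equals 24 / 6 = 4 sessions at the cap, so it matches neither count, but a ceiling may lie above the most that can occur. If the DECT truly replaced the SECT, the net added dose would fall below 6 cGy by the dose of the omitted scan, which the documents do not give.

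**4. Scans and tube voltage.** Two scans (Section 5.1) lie within two or three (Section 1.3), so these do not contradict each other, and the 6 cGy cap in Section 1.3 is written to cover either number. The lowest voltage does differ, by 80 − 70 = 10 kVp. The dose cap is set on CTDIvol per session, and no endpoint or analysis is tied to the voltage.

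**5. Analysis.** Section 5.2.2 takes the SECT data for the virtual trial from one of the two DECT data sets, so one research acquisition supplies both sides of each comparison. Section 7.0 works from patients per site (20-25), a correlation of 0.5 between arms and a paired t-test with n = 20. None of these uses the number of sessions or asks whether a clinical CT was also done.

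**The case for a change.** The strongest case for acting is that Section 1.2 is current text and makes a categorical statement about what participants undergo. It does not present itself as a summary or give way to Section 5.1. A protocol should give one account of radiation exposure, and the correction would cost a few sentences. The Section 6.1 total, which is four sessions' worth, suggests that the number of acquisitions was never settled. The use of a DECT data set as the SECT in Section 5.2.2 does not remove the conflict either, because it concerns which images are analysed and not which scans patients receive.

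The conflict over replacement versus addition stands in full. The conflict over session count stands in weaker form. The mention of a single session can be read as saying that both plans come from one acquisition, which fits Section 5.2.2, and the later sessions are conditional on logistics. Even so, the word limiting participation is hard to explain away.

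The objection does not show a consequence. The added imaging, the higher dose and the possible repeats are disclosed in the procedures section, and the stated total exceeds what those procedures can deliver at the cap. The consent text is not among the documents, so no mismatch there can be inferred.

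**Conclusion.** The contradiction is real but clerical. One paragraph of the rationale is out of step with the procedures section and with three other sections. Its size is 1 session against up to 3, or 6 against 18 cGy at the cap, with a stated total of 24 cGy. The differences in tube voltage and scan count add nothing of substance: the first has no shown effect and the second is not a contradiction.

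No change to the plan follows. Staff working from Section 5.1 would not be misled, no stated dose limit is breached, and endpoints, sample size, power and the paired analysis are the same under either account. The paragraphs should be reconciled when the document is next edited, and the investigators alone can say which account is intended.

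This conclusion assumes that Section 5.1 is what is carried out, that the 6 cGy cap holds in every session, and that the consent text, which could not be checked, describes the imaging as additional.

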1.3 CT scanning equipment

State-of-the art commercially marketed CT simulators in the Department of Radiation Oncology will be used to acquire the research data needed for these projects. Currently, the systems available to this project include the Philips Brilliance Big Bore CT/simulator (16 detector rows and 85 cm bore) and the Siemens Confidence CT/simulator (20 detector rows and 80 cm bore).

In addition to acquiring medically-routine CT datasets, each patient subject will be scanned sequentially at two or three different beam energies (80 or 90 kVp, 100 kVp, 120 kVp, and/or 140 kVp) as part of this research study. These additional scans will be acquired utilizing the FDA-approved workflow and scanner operating modes. Sinogram data will be exported in raw, minimally processed form utilizing proprietary data export and processing tools provided to the investigators by the scanner vendors. In no case, will the additional local imaging dose (in terms of CTDI_{vol}) given to the patients by the two or three additional scans exceed 6 cGy per session.

1.4 Investigational image reconstruction algorithms and radiological quantity modeling tools

The overall goals of the grant application (1R01CA212638, “*Quantitative Dual-energy CT Imaging for Cancer Imaging and Radiation Therapy Applications*”), is to develop, validate and implement in clinically useful forms novel iterative dual-energy x-ray CT image reconstruction algorithms which incorporate realistic models of CT data acquisition physics, including beam hardening, scatter, detector response, and measurement noise. Our promising preliminary results demonstrate tissue cross section maps that are more accurate and have lower uncertainty than either post-reconstruction dual-energy CT mapping processes or state-of-the-art single-energy stoichiometric tissue property mapping. The connection between CT measurements and image intensity and PT-relevant radiological quantities is mediated by another innovation, the basis vector model (BVM) {Han, 2016}.

Immediately following acquisition of sequential dual energy images from patient subjects, raw sinograms without beam-hardening or scatter corrections will be extracted with the vendor’s support, in addition to vendor reconstructed images and preprocessed sinograms. The raw sinogram data will serve as input to the novel iterative DECT image reconstruction software.

2.0 OBJECTIVES

2.1 Primary Objectives

To evaluate 3D organ- and patient-specific distributions of various radiological quantities, including proton stopping powers.

2.2 Exploratory Objectives

To assess the impact of DECT tissue property mapping on

- a.) plan quality
- b.) dose-delivery accuracy, and
- c.) simulated patient outcomes

for locally advanced lung, H&N and brain tumor patients treated with proton therapy.

3.0 PATIENT SELECTION

1. Diagnosis of histologically proven primary or metastatic cancer requiring thoracic radiation therapy OR radiation therapy to the H&N or brain.
2. At least 18 years of age.
3. Planning to undergo proton- or photon-beam radiation therapy as part of the clinical management of the diagnosed cancer.
4. No implanted metallic objects excepting dental prostheses in the region to be scanned.
5. No IV or oral contrast medium within 24 hours prior to DECT image acquisition.
6. Not pregnant.
7. Able to understand and willing to sign an IRB-approved written informed consent document.

3.1 Inclusion of Women and Minorities

Both men and women and members of all races and ethnic groups are eligible for this trial.

4.0 REGISTRATION PROCEDURES

Patients must not start any protocol intervention prior to registration through the Siteman Cancer Center.

The following steps must be taken before registering patients to this study:

1. Confirmation of patient eligibility
2. Registration of patient in the Siteman Cancer Center database
3. Assignment of unique patient number (UPN)

4.1 Confirmation of Patient Eligibility

Confirm patient eligibility by collecting the information listed below:

1. Registering MD's name
2. Patient's race, sex, and DOB
3. Three letters (or two letters and a dash) for the patient's initials
4. Copy of signed consent form
5. Completed eligibility checklist, signed and dated by a member of the study team
6. Copy of appropriate source documentation confirming patient eligibility

4.2 Patient Registration in the Siteman Cancer Center OnCore Database

All patients must be registered through the Siteman Cancer Center OnCore database.

[figure not shown]
4.3 Assignment of UPN

Each patient will be identified with a unique patient number (UPN) for this study. All data will be recorded with this identification number on the appropriate CRFs.

5.0 STUDY PLAN

5.1 Experimental procedures and data to be acquired

Patient therapy will not be affected by enrollment in this study. Patients enrolling in this study will undergo additional sequential DECT scans in addition to their routine SECT or DECT scans by enrolling in this study, which will increase imaging dose to the patients. An additional two sequential scans of the thorax or H&N/brain will be acquired at scan settings ranging from 70kVp to 140 kVp (with or without additional filter) prior to initiating RT. Typically, the experimental DECT imaging data will be acquired prior to the clinically-necessary CT simulation study in the same session. Up to two additional experimental DECT imaging sessions should be scheduled when logistically feasible. For example, if a patient subject requires re-simulation, DECT scan data should be acquired prior to the clinical simulation study in the same session. Raw sinograms without beam-hardening or scatter corrections will be exported from the scanner and archived with the vendor's support. In addition, clinical SECT and DECT images acquired as part of routine RT planning will be collected for this study. For H&N and brain patients, the DECT scan volume should extend from the superior-most aspect of the cranium down to the suprasternal notch. For the thoracic patients, the scan volume should encompass the entire lung parenchyma (apices to base).

5.2 Study endpoints and methods of analysis

5.2.1 Definition of Virtual Clinical Trial

Figure 1 illustrates the concept of virtual clinical trial (VCT), a relatively new method in radiotherapy to evaluate the impact of a new technology with greatly reduced cost and risk to participating institutes and patients. The trial takes full advantage of computer modeling and simulation to evaluate the benefits of proposed technology in patient outcomes. In essence, the collected research images serve as an *in silico* model of the patient. On each patient, the impact of various planning and image reconstruction strategies can be assessed over the patient population.

